10.4.1.1.5 Certificate of Confidentiality

As part of study efforts to provide confidentiality of subject information, this study will obtain a Certificate of Confidentiality which helps to prevent forced disclosure of personally identifiable research information. The Certificate of Confidentiality allows investigators on this trial to refuse to disclose identifying information related to the research participants, should such disclosure have adverse consequences for subjects or damage their financial standing, employability, insurability or reputation. The informed consent includes the appropriate coverage and restrictions of the Certificate of Confidentiality.

10.4.1.2 Benefits

Subjects participating in the study may benefit from the study drugs, both of which are indicated in the use of the diseases. Additional possible benefits are tumor shrinkage and reduced morbidity.

10.5 CONSENT PROCESS AND DOCUMENTATION

All patients who are being considered for this trial will undergo informed consent prior to being enrolled on the trial. The PI or associate investigator will perform the consenting process. Patients and family members when applicable will be asked to read the consent and will be encouraged to ask questions. It will be stated clearly that participation in the research study is voluntary and that participants can withdraw from the study without losing benefits they would otherwise be entitled to. Patients will be enrolled after the consent document has been signed. The informed consent process will be documented in the patient's medical record and on the

informed consent document. This process will be performed by the local Principal Investigator or designee.

10.5.1 Procedure for Consent via Telephone

The informed consent document will be sent to the subject. An explanation of the study will be provided over the telephone after the subject has had the opportunity to read the consent form. The subject will sign and date the informed consent.

The original informed consent document will be sent back to the consenting investigator who will sign and date the consent form with the date the consent was obtained via telephone.

A fully executed copy will be returned via mail for the subject's records.

The informed consent process will be documented on a progress note by the consenting investigator.

11 PHARMACEUTICAL INFORMATION

11.1 SUNITINIB

11.1.1 Source

Sunitinib is manufactured by Pfizer and will be provided to the NIH CC Pharmacy under a CRADA.

11.1.2 Toxicity

(Please see package insert for a complete list of toxicities)

In over 10,000 subjects with solid malignant tumors diarrhea (52.4%), fatigue (49.0%), nausea (42.7%), decreased appetite (38.5%), vomiting (33.9%), palmar-plantar erythrodysesthesia syndrome (28.7%), hypertension (27.6%), stomatitis (26.0%), dysgeusia (25.9%), and mucosal inflammation (25.7%) were the most commonly reported treatment emergent adverse events.

Overall, 60.3% experienced treatment-related AEs of Grade 3, 4, or 5 severity; Grade 3 in 46.9% of subjects, Grade 4 and grade 5 in 11.9% and 1.6% of subjects respectively. The most commonly reported were neutropenia (13.5%), fatigue (9.2%), thrombocytopenia (8.6%), palmar-plantar erythrodysesthesia syndrome (7.4%), diarrhea (6.3%), hypertension (5.5%), and asthenia (5.0%).

Neutropenia (0.3%), fatigue (8.8%), palmar-plantar erythrodysesthesia syndrome (7.4%), thrombocytopenia (6.8%), diarrhea (6.1%); and hypertension (5.4%) were the most commonly reported treatment-related AEs of Grade 3 severity. Neutropenia (3.2%), thrombocytopenia (1.8%), and anemia (0.9%) were the most commonly reported treatment-related AEs of Grade 4 severity. Pulmonary embolism, cardiac failure, death, cerebral hemorrhage, renal failure, myocardial infarction, hepatic failure, gastrointestinal hemorrhage, multi-organ failure, respiratory failure, pneumonia, septic shock, cardiac arrest, sepsis, sudden death, tumor hemorrhage, and hemorrhage, were among the Grade 5 treatment-related AEs reported in at least 3 subjects.

Boxed Warning:

SUTENT has been associated with hepatotoxicity, which may result in liver failure or death. Liver failure has been observed in clinical trials (7/2281 [0.3%]) and post-marketing experience.

Liver failure signs include jaundice, elevated transaminases and/or hyperbilirubinemia in conjunction with encephalopathy, coagulopathy, and/or renal failure. Monitor liver function tests (ALT, AST, bilirubin) before initiation of treatment, during each cycle of treatment, and as clinically indicated. SUTENT should be interrupted for Grade 3 or 4 drug-related hepatic adverse events and discontinued if there is no resolution. Do not restart SUTENT if patients subsequently experience severe changes in liver function tests or have other signs and symptoms of liver failure.

Safety in patients with ALT or AST $>2.5 \times$ ULN or, if due to liver metastases, $>5.0 \times$ ULN has not been established.

11.1.3 Formulation and preparation

Sunitinib malate capsules consist of hard gelatin capsules containing sunitinib malate equivalent to 12.5, 25 and 50 mg sunitinib together with mannitol, croscarmellose sodium, povidone, and magnesium stearate.

11.1.4 Stability and Storage

Sunitinib – will be stored in a closed container at room temperature (15 to 30°C), away from heat, moisture, and direct light.

11.1.5 Administration procedures

Please see Section **3.2.1**

11.1.6 Incompatibilities

[figure not shown]
Co-administration of sunitinib with strong inhibitors of the CYP3A4 family (e.g., ketoconazole, itraconazole, clarithromycin, atazanavir, indinavir, nefazodone, nelfinavir, ritonavir, saquinavir, telithromycin, voriconazole) may increase sunitinib concentrations. Grapefruit may also increase plasma concentrations of sunitinib. A dose reduction for sunitinib should be considered when it must be co-administered with strong CYP3A4 inhibitors.

11.2 EVEROLIMUS

11.2.1 Drug substance

Chemical name	(1R,9S,12S,15R,16E,18R,19R,21R,23S,24E,26E,28E,30S,32S,35R)-1,18-dihydroxy-12-[(1R)-2-[(1S,3R,4R)-4-(2-hydroxyethoxy)-3-methoxycyclohexyl]-1-methylethyl]-19,30-dimethoxy-15,17,21,23,29,35-hexamethyl-11,36-dioxo-4-azatricyclo[30.3.1.0 ^{4,9}]hexatriaconta-16,24, 26,28-tetraene-2,3,10,14,20-pentaone
International non-proprietary name	Everolimus

11.2.2 Chemical structure

11.2.3 Source

Everolimus will be manufactured and provided to the NIH CC Pharmacy by Novartis under a Clinical Trials Agreement.

11.2.4 Toxicity

(Please see package insert for a complete list of toxicities)

Toxicity information is based on pooled safety data in cancer patients receiving everolimus (N=2470) in clinical studies including randomized, double-blind, placebo- or active comparator-controlled phase-III trials and phase-II studies related to the approved indications in oncology.

The most common ADRs (incidence $\geq 1/10$ and suspected to be related to treatment by the investigator) from the pooled safety data were (in decreasing order): stomatitis, rash, fatigue, diarrhea, infections, nausea, decreased appetite, anemia, dysgeusia, pneumonitis, hyperglycemia, weight decreased, pruritus, asthenia, peripheral edema, hypercholesterolemia, epistaxis, and headache.

The most common grade 3/4 adverse drug reactions (incidence $\geq 1/100$ to $< 1/10$ and suspected to be related to treatment by the investigator) were stomatitis, anemia, hyperglycemia, fatigue, infections, pneumonitis, diarrhea, asthenia, thrombocytopenia, neutropenia, dyspnea, lymphopenia, proteinuria, hemorrhage, hypophosphatemia, rash, hypertension, aspartate aminotransferase (AST) increased, alanine aminotransferase (ALT) increased and pneumonia.

The most common adverse events were stomatitis (in 64% of the patients in the everolimus group vs. 17% in the placebo group), rash (49% vs. 10%), diarrhea (34% vs. 10%), fatigue (31% vs. 14%), and infections (23% vs. 6%). The most common grade 3 or 4 drug-related adverse events were anemia, hyperglycemia, stomatitis, thrombocytopenia, diarrhea, hypophosphatemia, and neutropenia[55].

11.2.5 Formulation and preparation

Dosage forms:	• Tablets will be supplied in 2.5 mg, 5
---------------	--

	
mg, and 10 mg formulations
 
 • Dispersible tablets (also referred to as ‘tablets for oral suspension’): 2 mg, 3 mg and 5 mg. The dispersible tablet is prepared as a suspension of undissolved medicine that is mixed with water, and then taken by mouth. The suspension can be prepared in an oral syringe or small drinking glass.
Composition/excipients:	
 • Tablets: Everolimus drug substance, butylhydroxytoluene/butylated hydroxytoluene (BHT), magnesium stearate, lactose anhydrous/Anhydrous lactose, lactose monohydrate, hypromellose/hydroxypropyl methylcellulose, crospovidone • Dispersible tablets: Everolimus drug substance, butylhydroxytoluene/butylated hydroxytoluene (BHT), magnesium stearate, lactose monohydrate, hypromellose/hydroxypropyl methylcellulose, crospovidone, silica colloidal anhydrous /colloidal silicon dioxide, mannitol/D-mannitol, cellulose microcrystalline/microcrystalline cellulose The excipients comply with the requirements of the applicable compendial monographs European Pharmacopeia (Ph. Eur.), Unites States Pharmacopeia / National Formulary (USP/NF).

11.2.6 Stability and Storage

Everolimus tablets and everolimus tablets for oral suspension are stored at 25°C (77°F); with excursions permitted between 15°–30°C (59°–86°F). Store everolimus in the original container, and protect from light and moisture.

11.2.7 Administration procedures

See Section [3.2.2](#)

11.2.8 Hazards and precautions

The extent of absorption of everolimus through topical exposure is not known. Therefore, caregivers are advised to avoid contact with suspensions of everolimus tablets or dispersible tablets. Wash hands thoroughly before and after preparation of either suspension.

Abbreviated Title: Targeted Rx in Advanced NETs
Version Date: 01/15/2019

11.2.9 Incompatibilities

Co-administration of everolimus with strong CYP3A4-inhibitors (e.g., ketoconazole, itraconazole, voriconazole, clarithromycin, telithromycin, ritonavir, boceprevir, telaprevir) and strong CYP3A4 inducers (e.g., rifampin, rifabutin) is not recommended without close monitoring of everolimus whole blood trough concentrations. Grapefruit and grapefruit juice inhibit cytochrome P450 3A4 and P-gp activity and should therefore be avoided with concomitant use of everolimus. Please refer to Section [4.2.2](#)

13.1 APPENDIX A: PERFORMANCE STATUS CRITERIA

ECOG Performance Status Scale	
Grade	Descriptions
0	Normal activity. Fully active, able to carry on all pre-disease performance without restriction.
1	Symptoms, but ambulatory. Restricted in physically strenuous activity, but ambulatory and able to carry out work of a light or sedentary nature (e.g., light housework, office work).
2	In bed <50% of the time. Ambulatory and capable of all self-care, but unable to carry out any work activities. Up and about more than 50% of waking hours.
3	In bed >50% of the time. Capable of only limited self-care, confined to bed or chair more than 50% of waking hours.
4	100% bedridden. Completely disabled. Cannot carry on any self-care. Totally confined to bed or chair.
5	Dead.

13.2 APPENDIX B: PREGNANCY AND ASSESSMENTS OF FERTILITY

There are no adequate data from the use of everolimus in pregnant women. Studies in animals have shown reproductive toxicity effects including embryo-toxicity and fetotoxicity. The potential risk for humans is unknown. Everolimus should not be given to pregnant women unless the potential benefit outweighs the potential risk to the fetus. If a pregnancy occurs while on study treatment, the newborn will be followed for at least 12 months.

It is not known whether everolimus is excreted in breast milk. However, in animal studies everolimus and/or its metabolites readily passed into the milk of lactating rats. Women taking everolimus should therefore not breast-feed.

Women of childbearing potential

Women of child-bearing potential, defined as all women physiologically capable of becoming pregnant, must use highly effective contraception during the study and for 8 weeks after stopping treatment. Highly effective contraception is defined as either:

- Total abstinence: When this is in line with the preferred and usual lifestyle of the subject. [Periodic abstinence (e.g., calendar, ovulation, symptothermal, post-ovulation methods) and withdrawal are not acceptable methods of contraception]
- Sterilization: have had surgical bilateral oophorectomy (with or without hysterectomy) or tubal ligation at least six weeks before taking study treatment. In case of oophorectomy alone, only when the reproductive status of the woman has been confirmed by follow up hormone level assessment
- Male partner sterilization (with the appropriate post-vasectomy documentation of the absence of sperm in the ejaculate). [For female subjects on the study, the vasectomised male partner should be the sole partner for that subject].
- Use of a combination of any two of the following (a+b or a+c or b+c):
 - a. Use of oral, injected, implanted or other hormonal methods of contraception
 - b. Placement of an intrauterine device (IUD) or intrauterine system (IUS)
 - c. Barrier methods of contraception: Condom or Occlusive cap (diaphragm or cervical/vault caps) with spermicidal foam/gel/film/cream/vaginal suppository
- In case of use of oral contraception, women should have been stable on the oral agent before taking study treatment.

Male Contraception

Sexually active males must use a condom during intercourse while taking the drug and for 8 weeks after stopping treatment and should not father a child in this period.

A condom is required to be used also by vasectomised men in order to prevent delivery of the drug via seminal fluid.

Female partners of male patients must also be advised to use one of the following contraception methods: Use of (1) oral, injected, implanted or other hormonal methods of contraception, or (2) intrauterine device (IUD) or intrauterine system (IUS), or (3) prior male/female sterilization.

Fertility

Abbreviated Title: Targeted Rx in Advanced NETs
Version Date: 01/15/2019

The potential for everolimus to cause infertility in male and female patients is unknown. However, menstrual irregularities, secondary amenorrhea and associated luteinizing hormone (LH)/follicle stimulating hormone (FSH) imbalance has been observed. Based on non-clinical findings, male and female fertility may be compromised by treatment with everolimus.

13.3 APPENDIX C: PANEL OF 197 GENES TESTED FOR IN CLINICAL MOLECULAR PROFILING CORE (CLIA-COMPLIANT). GENES IMPLICATED IN NETS ARE IN BOLD.

Genes

ABL1	DMBT1	KRAS	RNF2
ACN9	DNMT3A	KRT20	RPS15
ACVR1B	DPYD	MAG11	RUNX1
AKT1	EGF	MAP2K4	SCLC1
ALK	EGFR	MEN1	SDHA
APC	EGR3	MET	SDHAF1
ARHGEF2	EIF4G2	MGMT	SDHAF2
ARID1A	EML4	MIB1	SDHB
ASXL1	ENO1	MKI67	SDHC
ATM	ENO2	MLH1	SDHD
ATRX	ERBB2	MPL	SELT
BAG3	ERBB3	MSH2	SETD2
BAI3	ERBB4	MSH6	SLC38A1
BAP1	ERG	MUC1	SLC6A2
BCAN	EZH2	MUC17	SLTM
BCL2	F10	MUC2	SMAD4
BRAF	FAM123B	MUC3A	SMARCA4
BRCA1	FBXW7	MUTYH	SMARCB1
BRCA2	FGFR1	MVP	SMO
CA12	FGFR2	MYC	SMOX
CA9	FGFR3	MYD88	SMUG1
CALU	FH	NAT1	SOCS1
CARD11	FHIT	NAT2	SRC
CBL	FLCN	NES	SST
CCND1	FLT3	NF1	STC1
CD34	FOXL2	NF2	STK11
CDC73	FZRI	NOTCH1	SUFU
CDH1	GATA1	NOTCH2	SYP
CDK4	GATA2	NPM1	TCF7L2
CDKN2A	GATA3	NRAS	TET2
CDX2	GFAP	PBRM1	TFE3
CEACAM7	GNA11	PCNA	TFEB
CEBPA	GNAQ	PDGFRA	TMEM97
CES3	GNAS	PDZD4	TNFAIP3
CHDM	GRP	PGR	TNFSF13
CRLF2	GSTM1	PHOX2B	TP53

CSF1R	HIVEP3	PIK3CA	TPD52L2
CSF3	HNF1A	PMS2	TPM4
CTNNA1	HRAS	PPP2R1A	TSC1
CTNNB1	IDH1	PRCC	TSC2
CUL2	IDH2	PRKAR1A	TSHR
CYLD	IFNA1	PTCH1	TYK2
CYP11A1	IGKV1D-43	PTEN	VHL
DAXX	IL2	PTGS2	VIM
DCC	ITGB5	PTPN11	WT1
DES	JAK1	RB1	WTS
DIRAS1	JAK2	REEP5	XRCC1
DIRC2	JAK3	RET	ZNF135
DKK3	KDR	RNF139	
DLD	KIT		

13.4 APPENDIX D: PATHWAY ANALYSIS OF 193 MAPPED GENES USING INGENUITY PATHWAY ANALYSIS*

Ingenuity Canonical Pathways	Molecules
AMPK Signaling	SRC,TSC1,PIK3CA,PPP2R1A,GNAS,AKT1,STK11,TSC2,SMARCA4,ATM,PRKAR1A
Angiopoietin Signaling	PIK3CA,AKT1,NRAS,PTPN11,HRAS,KRAS,ATM
EGF Signaling	MAP2K4,SRC,PIK3CA,JAK1,AKT1,EGF,HRAS,ATM,EGFR
Endothelin-1 Signaling	BRAF,MYC,SRC,PIK3CA,GNAS,NRAS,GNA11,GNAQ,HRAS,KRAS,PTGS2,ATM
Ephrin A Signaling	PIK3CA,PTPN11,ATM
Ephrin B Signaling	GNAS,CBL,GNA11,GNAQ,HRAS,CTNNB1
Ephrin Receptor Signaling	SRC,GNAS,AKT1,NRAS,PTPN11,GNA11,ABL1,GNAQ,EGF,HRAS,KRAS,JAK2
ErbB Signaling	MAP2K4,PIK3CA,AKT1,NRAS,ERBB4,EGF,HRAS,KRAS,ERBB3,ERBB2,ATM,EGFR
ErbB2-ErbB3 Signaling	PIK3CA,NRAS,TYK2,HRAS,KRAS,ERBB3,CCND1,PTEN,MYC,AKT1,ERBB2,JAK3,ATM
ErbB4 Signaling	PIK3CA,AKT1,NRAS,ERBB4,HRAS,KRAS,ATM
ERK/MAPK Signaling	BRAF,MYC,SRC,PIK3CA,PPP2R1A,NRAS,HRAS,KRAS,ATM,PRKAR1A
ERK5 Signaling	MYC,SRC,AKT1,NRAS,PTPN11,GNAQ,EGF,HRAS,KRAS,EGFR
Erythropoietin Signaling	SOCS1,SRC,PIK3CA,AKT1,NRAS,CBL,HRAS,KRAS,JAK2,ATM
Inhibition of Angiogenesis by TSP1	MAP2K4,TP53,AKT1,KDR
Insulin Receptor Signaling	TSC1,PIK3CA,JAK1,NRAS,HRAS,KRAS,JAK2,PTEN,AKT1,CBL,PTPN11,TSC2,PRKAR1A,ATM
mTOR Signaling	TSC1,PIK3CA,PPP2R1A,AKT1,NRAS,EIF4G2,STK11,TSC2,RPS15,HRAS,KRAS,ATM
p38 MAPK Signaling	MAP2K4,TP53,MYC,DAXX
PDGF Signaling	MYC,MAP2K4,SRC,PIK3CA,NRAS,JAK1,TYK2,PDGFRA,ABL1,HRAS,KRAS,JAK2,JAK3,ATM
PI3K/AKT Signaling	TP53,TSC1,PIK3CA,JAK1,NRAS,TYK2,HRAS,KRAS,JAK2,CCND1,PTEN,BCL2,PPP2R1A,AKT1,TSC2,PTGS2,JAK3,CTNNB1
Protein Kinase A Signaling	GNAS,PTCH1,GNAQ,HNF1A,PTEN,BRAF,PTPN11,DCC,SMO,SMAD4,PTGS2,CTNNB1,TCF7L2,PRKAR1A
PTEN Signaling	PIK3CA,NRAS,FGFR1,HRAS,FGFR2,KRAS,CCND1,PTEN,BCL2,FGFR3,MAGI1,CBL,AKT1,PDGFRA,KDR,EGFR
Role of Tissue Factor in Cancer	TP53,SRC,PIK3CA,NRAS,GNA11,GNAQ,HRAS,KRAS,JAK2,PTEN,F10,AKT1,PTPN11,ITGB5,EGFR,ATM
VEGF Family Ligand-Receptor Interactions	PIK3CA,AKT1,NRAS,HRAS,KRAS,KDR,ATM
VEGF Signaling	SRC,PIK3CA,AKT1,NRAS,PTPN11,HRAS,KRAS,KDR,ATM,BCL2
Wnt/ β -catenin Signaling	TP53,CDKN2A,SRC,GNAQ,CCND1,HNF1A,APC,ACVR1B,MYC,CDH1,PPP2R1A,AKT1,DKK3,SMO,CTNNB1,TCF7L2

13.5 APPENDIX E: COLLECTION/RECORDING OF BLOOD PRESSURE INFORMATION

1.0 General Guidelines

- 1.1 Frequency of monitoring. Blood pressure (BP) should be monitored at baseline, and then at every clinic visit, as well as at home during weeks when there is no clinic visit.
- 1.2 Data recording. All required data should be recorded in the appropriate CRF or on the patient's blood pressure monitoring diary, as appropriate. **The following data are required at baseline and at each subsequent assessment:**
 - Assessment date and time
 - Pulse
 - Systolic and diastolic BP
- 1.3 Risk factors for hypertension (assess and record data in baseline history/physical CRF)
 - Diabetes (type 1 or type 2)
 - Renal disease (specify on CRF)
 - Endocrine condition associated with HTN (specify on CRF)
 - Use of steroids or NSAIDs (specify all concomitant meds)
 - Underlying cardiovascular condition – specify (*i.e.*, ischemic heart disease)

2.0 Baseline data collection (at study entry)

- 2.1 All patients
 - Current BP
 - Proteinuria, if present
- 2.2 Patients with preexisting hypertension (*i.e.*, those for whom “hypertension” is entered as a concomitant condition at study entry, or those who are currently receiving therapy with antihypertensive medication) – also record:
 - Date of HTN diagnosis (original)
 - Type HTN (essential or secondary)
 - CTCAE grade of HTN (at time of study entry)
 - Trade name, drug class*, dose, dose frequency, start/stop dates/ongoing of the following:
 - Antihypertensive agents taken at study entry
 - Antihypertensive agents taken in past (e.g., discontinued for toxicity, lack of efficacy)

3.0 Follow up BP data collection (during study)

- 3.1 All patients (at each clinic visit)
 - Current BP
 - Proteinuria, if present
- 3.2 Patients with treatment-emergent hypertension [defined as BP increase of >20 mmHg (diastolic) OR systolic BP >139 OR diastolic BP > 90 (if previously normal or grade 1 per CTCAE v4) – record at time of hypertension diagnosis and at all subsequent clinic visits:
 - BP changes from baseline (or from previous assessment) (specify CTCAE

grade changes)

- Hypertension-related symptoms as reported by patient (*e.g.*, headache)
- Other relevant changes associated with development of hypertension (*e.g.*, ECG abnormalities)
- Trade name, drug class*, dose, dose frequency, start/stop dates/ongoing of currently prescribed antihypertensive agents

3.3 Patients with pre-existing hypertension at study entry – record at each clinic visit

- BP changes from previous clinic visit (specify CTCAE grade changes)
- Hypertension-related symptoms reported by patient (*e.g.*, headache)
- Other relevant changes associated with development of hypertension (*e.g.*, ECG abnormalities)
- Changes in antihypertensive medications since last assessment (*e.g.*, dose change, add/discontinue drug)

*Classes of antihypertensive drugs include ACE inhibitors, calcium channel blockers, alpha blockers, beta blockers, diuretics, angiotension II receptor antagonists.

13.6 APPENDIX F: PATIENT DRUG ADMINISTRATION DIARY

13.6.1 Sunitinib

Patient Name _____ **Study ID** _____

Please complete this form and return to the research nurse or doctor every cycle

You will take: Sunitinib **Dose:** _____ mg each morning with or without food. Be advised to drink plenty of water while you are on sunitinib.

You will only need to take your blood pressure once per week. Please be sure you are seated when you take the measurement.

DAY	DATE	TIME TAKEN	Blood Pressure	COMMENTS (side effects or missed doses)
1				
2				
3				
4				
5				
6				
7				
8				
9				
10				
11				
12				
13				
14				
15				
16				
17				
18				
19				
20				
21				
22				
23				
24				
25				
26				

Abbreviated Title: Targeted Rx in Advanced NETs
Version Date: 01/15/2019

27				
28				

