3.2 STUDY DRUG ADMINISTRATION

3.2.1 Sunitinib Treatment and dose

Patients on Arm 1 will be treated with oral sunitinib at a starting dose of 37.5 mg once daily.

Patients will take sunitinib once daily in the morning, with or without food, as desired. Patients should be advised to drink plenty of water or take rehydration fluids to avoid dehydration if

diarrhea occurs. If a dose is missed the subject will be instructed to take the next dose as scheduled.

- 3.2.1.1 Because hypertension is a known and potentially serious adverse event associated with sunitinib maleate treatment, patients will have their blood pressure monitored and recorded at baseline and weekly during sunitinib treatment either at the doctor's office or using any calibrated electronic device (such as those found at a local drug store or pharmacy). **Appendix E** detail the collection and recording of blood pressure related information.
- 3.2.1.2 Patients with bulky solid tumors should be monitored closely for pneumothorax, intestinal fistulae, or intestinal perforation in the event of rapid tumor destruction.
- 3.2.1.3 Patients should be alerted to the possibility that sunitinib capsules can cause a yellow discoloration of the skin on direct contact. If this happens, the patient should wash immediately with soap and water.
- 3.2.1.4 Thyroid function (free T4, T3 and TSH) will be monitored at every cycle).

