3.2.3 CCR Self-Administered Study Drugs Policy

All oral self-administered investigational agents will be properly accounted for, handled, and disposed in accordance with existing federal regulations and principles of Good Clinical Practice. All oral study drugs will be recorded in the patient diary found in [Appendix F](#). This will be used as a memory aide for subjects. The clinical research team will maintain the primary source record.

Subjects should be asked to bring the diary as well as unused study agent and empty containers with them at each study visit. If a subject goes off study while at home, the research nurse will ensure and document the return of the unused oral investigational agents from the participant.

Unused investigational study agents will be disposed and destroyed per CC pharmacy SOPs.

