
Persistent Grade 3 Severe Systolic ≥ 160 Diastolic ≥ 100
 
Protocol-specific guidance supersedes any other management guidelines, including CTCAE v4
	
HOLD sunitinib until systolic BP ≤ 159 and diastolic BP ≤ 99.
 
BP management is identical to that for Grade 2 (see steps 1-4 above) with 2 major exceptions:
 
1) If systolic BP >180 or diastolic BP >110 and the patient is symptomatic: optimal management with intensive IV support in ICU; STOP sunitinib and notify hospital staff that stopping sunitinib may result in a decrease in BP and
 
2) If systolic BP >180 or diastolic BP >110 and the patient is asymptomatic, 2 new anti-hypertensives must be given together in step 1 (and dose escalated appropriately as in step 1).
 
NOTE: Stopping or reducing the dose of sunitinib is expected to cause a decrease in BP the treating physician should monitor the patient for hypotension and adjust the number and dose of antihypertensive medication(s) accordingly
	
BP should be monitored as recommended by the treating physician unless the patient is symptomatic with systolic BP >180 or diastolic BP >110 in which case, monitoring should be intensive.
	
HOLD sunitinib until systolic BP ≤ 159 and diastolic BP ≤ 99.
 
In most circumstances, if BP cannot be controlled after an optimal trial of anti-hypertensive medications, consider either 1 dose reduction of sunitinib or stopping sunitinib. HOWEVER, if the patient requires hospitalization for management of symptomatic systolic BP >180 or diastolic BP >110, permanently discontinue sunitinib or if BP is controlled, re-start sunitinib at 1 lower dose level after consultation with the study Principal Investigator

Grade 4 Life-threatening consequences of hypertension
	
Optimal management with intensive IV support in ICU; STOP sunitinib and notify hospital staff that stopping sunitinib may result in a decrease in BP
	
Intensive
	
Permanently discontinue sunitinib or if BP is controlled, re-start sunitinib at 1 lower dose level after consultation with the study

Grade (CTCAE v4)	Antihypertensive Therapy	Blood Pressure Monitoring	Sunitinib Dose Modification
			Principal Investigator

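### From cycle 3 on, home blood pressures on sunitinib go into a diary returned once per cycle with no call-in value, so a Table 6 hold trigger could go unseen for up to about 14 days (21 if the visit is a week late)

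*Combined protocol and SAP*

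**What the plan says.** Section 3.2.1.1 calls hypertension a known and potentially serious effect of sunitinib. It requires blood pressure to be "monitored and recorded at baseline and weekly during sunitinib treatment", either at a doctor's office or "using any calibrated electronic device". Appendix E (item 1.1) asks for a reading at each clinic visit, "as well as at home during weeks when there is no clinic visit". Item 1.2 sends the data to the case report form or the patient's "blood pressure monitoring diary, as appropriate".

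The sunitinib diary in Appendix F (13.6.1) tells the patient: "You will only need to take your blood pressure once per week". It also says: "Please complete this form and return to the research nurse or doctor every cycle". Section 3.2.3 adds: "Subjects should be asked to bring the diary as well as unused study agent and empty containers with them at each study visit".

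The Study Calendar (section 3.4) sets 28-day cycles and lets a visit fall up to 7 days early or late. Cycles 1 and 2 list Day 1 and Day 15. The Cycle N row, which I read as cycle 3 onward, lists Day 1 only.

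Table 6 (section 3.3.1.1) starts antihypertensive treatment at persistent 140-159 systolic or 90-99 diastolic. At persistent systolic ≥160 or diastolic ≥100 the instruction is "HOLD sunitinib until systolic BP ≤ 159", with a matching diastolic limit of 99. The table does not define persistent.

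**The concern.** The plan requires the readings that would reveal a hold-level pressure, but describes no route for a home reading to reach staff before the next visit. A patient who self-measures and follows the diary and calendar exactly could keep taking daily sunitinib at a pressure where Table 6 says to hold and treat. Patients without symptoms are the most exposed, because nothing in the available text prompts them to call.

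This sits badly with the pace that Table 6 sets elsewhere. Antihypertensive doses are to be stepped up every 24-48 hours, and protocol therapy stops if managing hypertension needs a delay of more than 2 weeks. The protocol also writes explicit contact rules for everolimus patients: a missed dose (section 3.2.2) and the first mouth irritation (section 4.1.2.6). Sunitinib blood pressure has no counterpart.

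**Working it through.** The plan gives no figure for this delay, so there is none to reproduce. The check is calendar arithmetic.

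**Inputs from the plan**
- Cycle length 28 days, visit window 7 days either way (section 3.4). The next Day 1 visit is therefore Day 29 of the current cycle, Day 22 if early and Day 36 if late.
- From cycle 3, one listed visit per cycle (section 3.4).
- Weekly readings, at home between visits (section 3.2.1.1 and Appendix E).

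**Assumptions**
- Persistent means two consecutive weekly home readings at the Grade 3 level.
- Home readings fall every 7 days counted from the visit: Days 8, 15 and 22, plus Day 29 if the visit is late.

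**Formula:** wait = day of next visit − day of the second reading.

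| Pair of home readings | Visit 7 days early (Day 22) | On time (Day 29) | 7 days late (Day 36) |
|---|---|---|---|
| Days 8 and 15 | 22 − 15 = 7 | 29 − 15 = 14 | 36 − 15 = 21 |
| Days 15 and 22 | 22 − 22 = 0 | 29 − 22 = 7 | 36 − 22 = 14 |
| Days 22 and 29 | does not arise | Day 29 is the visit | 36 − 29 = 7 |

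**Sensitivity**
- *Reading day.* The diary fixes only the weekly frequency. If home readings can fall on any day of the week, the second reading falls between Day 15 and Day 28 before an on-time visit. The wait is then 29 − 28 = 1 to 29 − 15 = 14 days. The maximum does not change; the minimum does.
- *Clinic reading as the first of the pair.* Days 1 and 8 would give 29 − 8 = 21 days on time and 36 − 8 = 28 late, but staff would already have seen the first value.
- *One high reading.* Day 8, 15 or 22 waits 21, 14 or 7 days on time. This is not clearly a Table 6 trigger, since the table asks for persistence.
- *Cycles 1 and 2.* Home readings on Days 8 and 22 are separated by the Day 15 visit, so two in a row never fall between on-time visits.

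**Other possible routes to staff**
- The weekly team meeting (section 7.4.1) and two-weekly data entry (section 6.1) include no step that obtains home readings.
- Physician-set monitoring in Table 6 begins once raised pressure is known.
- Appendix E's follow-up items are recorded at hypertension diagnosis and at clinic visits.

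**Frequency.** Section 11.1.2 gives a pooled 5.5% for treatment-related hypertension of Grade 3-5. Applied to 44 sunitinib patients this is 0.055 × 44 = 2.4; applied to all 120 it is 6.6. Both count every severe event, whenever and however detected. The share that starts between visits from cycle 3 on, is self-measured and causes no symptoms is not given and cannot be derived.

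**The case against.** The strongest objection is that this concerns a missing patient instruction while the consent pages, a natural place for one, have been removed. That stands as a limit. A reader might infer that patients receive no call-in advice at all; the documents do not support that. What can be shown is narrower: the diary, section 3.2.1.1, Table 6 and Appendix E carry no threshold. A consent-form line would not change what is printed on the page the patient holds when taking the reading.

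Second, the delay depends on reading days and visit timing. A reader might infer a fixed wait of 7-14 days, or 14-21 with a late visit. Those ranges require set reading days, leave out early visits, and ignore the extra Day 29 reading before a late visit. Only the upper limits survive, and they still rest on the two-reading meaning of persistent.

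Third, a reader might take 2.4 of 44 or 6.6 of 120 as the number of patients at risk. Neither measures the gap. The pooled rate may also not carry over: patients here start at 37.5 mg, while section 1.2.3.1.3 refers to a recommended 50 mg dose.

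Fourth, safeguards exist. Entry excludes uncontrolled pressure above 150/100 (section 2.1.2.1). Weekly office readings are allowed and are unaffected. Known Grade 2 hypertension in the first 8 weeks should bar escalation to 50 mg (section 3.3.1). Nothing forbids an earlier call. These narrow the gap, but none brings an unreported home reading to staff.

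**Conclusion.** The point holds as a gap in safety monitoring that is worth closing. On the two-reading assumption, a Table 6 hold trigger from self-measured readings in cycle 3 or later can go unseen for up to about 14 days with an on-time visit, up to 21 days with a visit 7 days late, and about 7 days or less with a visit 7 days early. The exact wait depends on the reading day. The conclusion is conditional on the removed consent pages, does not apply to office readings, and supports no estimate of how many patients would be affected. It has no bearing on the sample size or power. Confidence is medium.

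**What to change.** Print the following on the Appendix F sunitinib diary, and state it in section 3.2.1.1 and Appendix E:

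- Systolic ≥160 or diastolic ≥100: repeat the reading and phone the research nurse the same day.
- Systolic >180 or diastolic >110 with symptoms: seek urgent care.
- Two weekly readings in a row at ≥140 systolic or ≥90 diastolic: phone the research nurse.

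The third line is needed because Table 6 starts treatment at persistent Grade 2. A call rule at 160/100 alone would leave that trigger unreported until the visit. All the cut-offs are already in Table 6, and whether a pressure counts as persistent stays with the physician.

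The cost is a diary reprint and a few sentences in two sections, with no new visits, tests or analyses. The downside is some extra calls to existing staff, including for readings that settle on repeat.
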